2.0 Scientific Endpoints

2.1 Describe the scientific endpoint(s), the main result or occurrence under study.

*NOTE: Scientific endpoints are outcomes defined before the study begins to determine whether the objectives of the study have been met and to draw conclusions from the data. Include primary and secondary endpoints. Some example endpoints are: reduction of symptoms, improvement in quality of life, or survival. Your response should **not** be a date.*

Response:

Our primary outcome is that Buzzy will have a greater degree of reduction of anxiety and pain levels compared to vapocoolant or placebo.

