3.0 Background

3.1 Provide the scientific or scholarly background, rationale, and significance of the research based on the existing literature and how it will contribute to existing knowledge. Describe any gaps in current knowledge. Include relevant preliminary findings or prior research by the investigator.

Response:

Among pediatric patients, phlebotomy and intravenous cannulation are two important sources of self-reported pain in the pediatric ED. Unmanaged needle stick pain has been associated with needle phobia, greater pain with future sticks; anxiety associated with other medical procedures, healthcare avoidance and increased adult pain sensitivity (Lunoe, 2014; Cohen 1997; Hamilton, 1995; Pate, 1996). Various methods have been proposed for management of acute pain associated with these medical procedures. Pharmacological methods include EMLA, lidocaine and ethyl chloride (vapocoolant). Behavioral methods such as information provision, distraction, sensory focusing, and cognitive behavioral therapy (CBT) have also been utilized (Blount, 2009). Optimization of pain control during phlebotomy and IV catheterization in the Pediatric ED is essential in an effort to avoid the aforementioned adverse effects of needle insertion. In the pediatric ED, quick acting methods are favored over those requiring time to act such as EMLA and CBT.

Vapocoolants, volatile refrigerated liquids such as ethyl chloride, are a frequent choice in many pediatric EDs, including our own, prior to phlebotomy or IV cannulation. Despite this, research has offered conflicting results as to their efficacy. Hogan and her colleagues conducted a systematic review of Vapocoolant in both children and adults and concluded that their "...results demonstrated that Vapocoolants are ineffective in children when compared to placebo or no treatment" (Hogan ,2014). Shah, Taddio & Rieder have hypothesized that the sensation of cold on their skin is perceived by children as painful (Shah, 2009).

Recently several labs have introduced hand held devices based on Melzack and Wall's Gait Control theory (Melzack 1965) which asserts that activation of non-nociceptive fibers can interfere with signals from pain fibers thereby inhibiting pain. This theory helps to explain why rubbing or massaging a painful area of skin can lessen the pain. One such device is the Buzzy.. The Buzzy is a vibrating palm-sized device with removable ice wings developed by MMJ Labs Atlanta, GA.

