10.0 Procedures Involved

10.1 Provide a description of all research procedures or activities being performed and when they are performed once a subject is screened and determined to be eligible. Provide as much detail as possible.

NOTE: This should serve as a blueprint for your study and include enough detail so that another investigator could pick up your protocol and replicate the research. For studies that have multiple or complex visits or procedures, consider the addition of a schedule of events table in in your response.

Response:

Randomization of subject into one of the three study arms

There will be three arms of this study with each arm testing a different pain reducer: Buzzy Bee, Vapocoolant, and placebo. We will use a sham device e.g. a band around the arm for placebo control.

After obtaining informed consent, the patients will be randomized into one of the three groups following a randomization table created by a statistician. Whichever intervention is randomly selected will be performed on patient prior to the needle stick.

These methods have been used in the ED as part of routine procedures to help patient for pain relief from a needle stick, the RNs are familiar with these methods. However, for the purpose of this study, the training videos will be uploaded in the Kaleidoscope Talent management for RNs to review the procedure and help them to refresh their memories.

Videotaping of subject

Using a camera, an ED research assistant will videotape subject's whole body including the facial expression while phlebotomy and IV catheter placement is performed for scoring of the PBCL. We will tape the entire venipuncture procedure starting from sterilization and ending at the time when the venipuncture is completed. If the first venipuncture procedure attempt is failed, we will not tape the second attempt. This subject will be withdrawn from the study.

Obtaining pain scores from subject and legal guardian using the Faces Pain Scale-Revised instrument

Before and after the venipuncture procedure, we will ask the legal guardian and subject to complete a Faces pain scale revised form. Since the revised form is validated to use for both adult and children, the same document will be used for the legal guardian and children for this study. This document is attached with this submission.

Reviewing of the videotape

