17.0 Data Management and Analysis

17.1 *Describe the data analysis plan, including any statistical procedures. This section applies to both quantitative and qualitative analysis.*

Response:

All data analyses will be performed with SAS (version 9.2; SAS Institute, Inc., Cary, NC) and R (version 3.0.3) software. Chi-square and Fisher's exact test will be used to compare adverse events (e.g., systemic reaction, anaphylaxis, SOB, dyspnea, excess bleeding or hematoma formation), venipuncture and catheterization first attempt success, and number of patients with no to mild pain during needle insertion.

The Kruskal-Wallis test will be used to compare each of the two observers' assigned scores on the PBCL across three time periods: pre, procedure and post-procedure. Pre-procedure is defined as the time period prior to needle insertion including the placement of Vapocoolant, pain control or sham device up to needle insertion. The procedure period is defined as needle insertion through withdrawal. Post-procedure is defined as the 2 minute time period after needle withdrawal. Only patient and observer pain scores will be used for first-time needle insertion. If first attempt is failed, subject will be withdrawn from the study. Comparisons of pain scores of the five intervention groups to placebo (sham device) will be analyzed via ANOVA.

17.2 If applicable, provide a power analysis.

NOTE: This may not apply to certain types of studies, including chart/records reviews, survey studies, or observational studies. This question is asked to elicit whether the investigator has an adequate sample size to achieve the study objectives and justify a conclusion.

Response:

For chi-square analysis, based on a medium effect size of 0.3, alpha of 0.05, degree of freedom of 8, and 80% power it is estimated we will need a total of 168 subjects (56 per group). (*QFAB Bioinformatics*. 2015)

17.3 Describe any procedures that will be used for quality control of collected data.

Response:

Our RA will double check the data form to assure accuracy and completeness of data collection, if there is any missed data point, the RA will fill in the missing information immediately.

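### The primary outcome is an undefined reduction, and the only PBCL reference period offered is scored while the randomised intervention is being applied

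*Combined protocol and SAP*

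**What the plan says.** Section 2.1 gives the only primary outcome: "Our primary outcome is that Buzzy will have a greater degree of reduction of anxiety and pain levels compared to vapocoolant or placebo". It does not say which scale is meant, when it is scored, or what the reduction is measured from.

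Section 17.1, repeated at the end of the document after section 32, divides the PBCL into three periods. The pre-period ends at insertion and is described as "including the placement of Vapocoolant, pain control or sham device up to needle insertion". For the other two: "The procedure period is defined as needle insertion through withdrawal" and "Post-procedure is defined as the 2 minute time period after needle withdrawal". The test is stated as follows: "The Kruskal-Wallis test will be used to compare each of the two observers' assigned scores on the PBCL across three time periods". A separate sentence assigns ANOVA to comparisons of pain scores with sham. Neither sentence mentions a change score or a baseline covariate.

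Section 10.1 places randomisation after consent and the allocated intervention before the stick. Child and guardian complete the FPS-R "Before and after the venipuncture procedure". The section does not say whether the first form is completed before or after the device or spray is applied.

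Section 3.1 cites a hypothesis that "the sensation of cold on their skin is perceived by children as painful". Buzzy is used with ice wings (section 1.1), and the sham is a band around the arm (section 10.1).

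**The concern.** A reduction needs a starting point. With scores labelled pre, procedure and post, the obvious candidate is the pre-period. That score is not a baseline, because it is recorded after randomisation and its definition takes in the application of the treatment under test. If applying one intervention distresses children, that arm starts higher and shows a larger fall, or a smaller rise, than its score during the stick would justify. If applying it soothes them, the arm is penalised.

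Because section 2.1 is not tied to any test in section 17.1, the choice between change from pre and the procedure-period score could be made after the data are seen. Read literally, the Kruskal-Wallis sentence compares periods rather than arms, so the plan also does not clearly contain the comparison that answers the question: how the three arms differ while the needle is in.

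**Working it through.** **The plan's own figure.** Section 17.2 uses a chi-square test with w = 0.3, alpha 0.05, 8 degrees of freedom and 80% power. The noncentrality is N × 0.3². The smallest N reaching 80% is 167, which rounds up to 168 for three equal arms; power at 168 is 80.3% (noncentrality 168 × 0.09 = 15.12). The figure reproduces. It uses no SD, correlation or change score, so it does not bear on this point either way.

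**Inputs for the illustration.** From the documents: 56 per arm and alpha 0.05. Assumed, because the documents do not give them: SD 1 for each score; pre/procedure correlation r; a shift b, in SD units, of the pre-period score in one arm; and no true difference during the stick. One two-sided pairwise t-test (110 df, noncentral t) stands in for whatever test would be applied to a change.

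**Change from pre.** The variance of procedure minus pre is 2(1 − r). The standard error of the difference between two arms is √[2(1 − r)] × √(2/56), and √(2/56) = 0.189. The spurious difference equals b.

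| r | b (SD) | Standard error | b / SE | False-positive rate |
|---|---|---|---|---|
| 0.5 | 0 | 0.189 | 0 | 5% |
| 0.5 | 0.05 | 0.189 | 0.26 | 5.8% |
| 0.5 | 0.1 | 0.189 | 0.53 | 8.2% |
| 0.5 | 0.3 | 0.189 | 1.59 | 35.0% |
| 0.3 | 0.2 | 0.224 | 0.89 | 14.4% |
| 0.7 | 0.3 | 0.146 | 2.05 | 52.9% |

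**Pre-period as covariate.** Adjustment shrinks the bias to r × b but does not remove it. At r = 0.5 and b = 0.3 the bias is 0.15 SD. The standard error is √(1 − 0.25) × 0.189 = 0.164, the ratio is 0.92, and the false-positive rate is 14.9%.

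**FPS-R before-score, if taken before application.** Randomisation balances it in expectation, so neither a change score nor a covariate adjustment is biased between arms. The effect is on precision only. For an assumed true difference of 0.5 SD and 56 per arm (normal approximation; noncentral t is less than one percentage point lower):

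- After-score alone: 0.5 / 0.189 = 2.65, power 75%.
- Change score: variance factor 2(1 − r). Power is 46% at r = 0, 61% at r = 0.3, 75% at r = 0.5 and 93% at r = 0.7. It is noisier than the after-score alone only when r is below 0.5.
- ANCOVA: variance factor 1 − r². At r = 0.5, 0.5 / 0.164 = 3.05, power 86%.

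**Passages that do not fit together.** Section 10.1 films from sterilization to the end of the venipuncture. That window contains the procedure period, may or may not contain placement of the intervention, and does not cover the two minutes after withdrawal. Sections 10.1 and 18.1 A describe one PBCL score per subject from each reviewer, whereas section 17.1 needs one per period.

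**The case against.** The strongest reply is that this criticises an analysis nobody planned. Section 17.1 contains no subtraction and no baseline. The three-period sentence can be read as comparing arms within each period, with the pre-period as a result of its own. Reduction can mean lower than the comparator, and other parts of the plan speak of levels: section 1.1 compares levels, and section 17.1 counts patients with little or no pain at insertion. This stands, to the extent that the plan cannot be said to prescribe change from pre. It does not remove the problem, because section 2.1 does not choose between these readings.

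A reader might also infer that vapocoolant would be flattered against Buzzy, since the cited remark about cold appears in the discussion of vapocoolants. The documents do not support a direction. Buzzy's ice wings are cold too, the net shift between the active arms could be zero or reversed, and the remark is a cited hypothesis, not data.

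A further tempting inference is that the FPS-R before-score is faulty because it contains no needle pain. Its absence is common to all arms and cancels between them. A fall from that score does not measure relief of needle pain, but the between-arm contrast is sound if the score precedes application. Section 10.1 leaves only that timing open.

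Finally, if placement is not filmed, less application distress may reach the pre-period score than its definition implies. The documents do not settle this.

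**Conclusion.** The concern holds in a limited form. The primary reduction is undefined and not linked to a test, and the PBCL pre-period is a post-randomisation score that cannot serve as a baseline. The plan permits a biased change-from-pre analysis without requiring one. The size cannot be fixed from the documents: at r = 0.5 the false-positive rate of one pairwise comparison runs from 5% with no shift, through 8% at 0.1 SD, to 35% at 0.3 SD. A reader should not take 35% as this trial's error rate, since it depends on an assumed shift, an assumed correlation and an analysis that the plan does not name. No bias in the FPS-R is shown; only its timing is missing. The point is worth acting on because it concerns the main comparison and the remedy is cheap.

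**What to change.** 1. Reword section 2.1 as a between-arm comparison of scores for the needle stick: Buzzy against vapocoolant and against placebo. Name one primary measure, either procedure-period PBCL or the post-procedure FPS-R with the child told to rate the needle pain. Keep anxiety as a stated outcome and say which instrument measures it.
2. In section 17.1, apply the test between the three arms on procedure-period PBCL, not across periods. Do not use the PBCL pre-period as baseline or covariate; report it by arm as distress during application.
3. In section 10.1, state that the FPS-R before-score is taken before the intervention is applied. In section 17.1, use it as an ANCOVA covariate for the post-procedure FPS-R. Under the assumptions above, that raises pairwise power from about 75% to about 86% at no cost in subjects.
4. Reconcile the three scoring periods in section 17.1 with the single score per subject in sections 10.1 and 18.1 A, and with the video window in section 10.1.

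The cost is small: wording changes, a fixed moment for a form already collected, and PBCL scoring by period, which adds some work for the two physicians reviewing the videos. The procedure period already lies within the filmed window. Reporting the pre-period in full, or the two minutes after withdrawal, may need longer filming.

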1.0 Objectives

1.1 Describe the purpose, specific aims, or objectives of this research.

Response:

The purpose of this study is to compare the anxiety and pain levels of patients when using Buzzy with ice wings, Vapocoolant, and placebo during venipuncture procedure in pediatric patients.

1.2 State the hypotheses to be tested, if applicable.

NOTE: A hypothesis is a specific, testable prediction about what you expect to happen in your study that corresponds with your above listed objectives.

Response:

We hypothesize that the Buzzy will provide greater pain relief based on patient self-report and parent report of their child's pain as well as independent observation when compared to Vapocoolant or placebo.

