5.0 Local Number of Subjects

5.1 Indicate the total number of subjects that will be enrolled or records that will be reviewed locally.

Response:

We will enroll 168 patients in the study with 56 in each arm.

5.2 If applicable, indicate how many subjects you expect to screen to reach your target sample (i.e. your screen failure rate).

Response:

We anticipate screening about 500 patients to reach our target sample.

5.3 Justify the feasibility of recruiting the proposed number of eligible subjects within the anticipated recruitment period. For example, how many potential subjects do you have access to? What percentage of those potential subjects do you need to recruit?

Response:

The Emergency Department at John R Oishei Children's Hospital has an annual volume of 45,000 to 50,000 patients, with at least 1/10 of them receiving venipunctures procedure including IV's line placement or phlebotomy procedure for various reasons. We anticipate that we can easily enroll 168 subjects within 24 months.

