This study will not include patients whose legal guardians do not speak English. Children with parents/legal guardians who cannot speak and read English will be encountered infrequently. They represent diverse language groups and translating consent documents as well as translating pain scale surveys into many languages would be impractical for this unfunded study. Meanwhile, it is impractical for us to have two people who speak the same non-English language during the recruitment phase with one being the person who obtains the consent and one being the witness per our IRB request at any given time.

By not including non-English speaking subjects in this study, we are not withholding any benefit from these patients. Meanwhile, we do not anticipate that we add any burden to the patients who are enrolled in the study.

The main purpose of this study is to compare the effectiveness of pain relief using different methods, the Buzzy, vapocoolant and placebo. Patient enrolled in the study will randomly assigned into one of the three different study groups, Buzzy Bee with ice wings, vapocoolant or placebo. For eligible patients that are not enrolled in the study, they may also receive buzzy, or vapocoolant intervention, depending on the bedside nurse's discretion, as these methods have been frequently used by our ED nurses to help patients for pain relief. So regardless weather a patient is enrolled in the study or not, he/she may receive the similar pain relief method for IV line placement or phlebotomy procedure.

Thus, we will exclude subjects whose legal guardians do not speak English from the study due to the above mentioned reasons. We believe that we will not withhold any benefit from non-participants, nor add any burden to the participants by not enrolling non-English speaking patients in the study.

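### The pain-score ANOVA describes five interventions against placebo in a trial of two interventions and a sham, and no planned test names the Buzzy-vs-vapocoolant contrast

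*Combined protocol and SAP*

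**What the plan says.** The design sections agree with one another. Section 5.1: "We will enroll 168 patients in the study with 56 in each arm". Section 6.4 has patients "randomly assigned into one of the three different study groups, Buzzy Bee with ice wings, vapocoolant or placebo". Section 10.1: "There will be three arms of this study with each arm testing a different pain reducer: Buzzy Bee, Vapocoolant, and placebo", with a band around the arm as the sham.

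The aims call for an active comparison. Section 1.1 sets out to "compare the anxiety and pain levels of patients when using Buzzy with ice wings, Vapocoolant, and placebo". Section 1.2 predicts "greater pain relief based on patient self-report and parent report" of the child's pain, "as well as independent observation when compared to Vapocoolant or placebo". Section 2.1: "Our primary outcome is that Buzzy will have a greater degree of reduction of anxiety and pain levels compared to vapocoolant or placebo". Section 3.1 again sets Buzzy against vapocoolant or placebo, and gives the lack of earlier comparisons of these commonly used methods as the gap to be filled.

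The analysis of pain scores in section 17.1 reads: "Comparisons of pain scores of the five intervention groups to placebo (sham device) will be analyzed via ANOVA". The same sentence stands, unchanged, in the Data Management and Analysis text that closes the document. Section 17.1 also plans chi-square or Fisher's exact tests, one of them on the number of patients with no or mild pain, and a Kruskal-Wallis test on each observer's PBCL scores over three time periods. Neither names a pair of arms, and no pairwise follow-up is given.

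**The concern.** There are two faults in one sentence. The number of interventions does not match the trial. And once the number is put right, the only between-arm comparison that the plan names is against sham, so the comparison between the two active methods is left without a test.

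A significant overall ANOVA would show that the three arms are not all alike; it would not show that Buzzy is better than vapocoolant. Two separate comparisons with sham do not show it either. Two equally effective treatments can fall on opposite sides of the significance threshold by chance, and a real difference between them is hidden when both beat sham. As written, the test for the active comparison would have to be chosen after the data are in hand.

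**Working it through.** **1. Number of groups.** Section 5.1 gives 168 patients at 56 per arm: 168 / 56 = 3 groups. Five interventions plus placebo would be 6 groups, which needs 6 × 56 = 336 patients, or leaves 168 / 6 = 28 per group. Neither figure appears in the documents.

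**2. The plan's own sample size (section 17.2).** Inputs: w = 0.3, alpha 0.05, 8 df, 80% power. Noncentrality = N × w² = 168 × 0.09 = 15.12; the critical value of chi-square on 8 df is 15.51; power = 80.3%. The smallest N is 167, or 168 as a multiple of three. The stated figure reproduces. Six groups cannot yield 8 df in a contingency table, because (6 − 1)(c − 1) = 8 has no whole-number solution; three groups can, as (3 − 1)(5 − 1) = 8. So the power paragraph also points to three arms.

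**3. Which planned test reaches Buzzy vs vapocoolant?**

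| Planned test (17.1) | Between-arm contrast named |
|---|---|
| ANOVA of pain scores | each intervention vs sham only |
| Chi-square/Fisher, no or mild pain | none; at most an overall three-arm test |
| Kruskal-Wallis, PBCL | none; compares periods, or at most all three arms within a period |

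**4. Illustration of what is at stake.** Assumptions, none from the documents: 56 analysed per arm, normal scores with SD 1, pooled variance (165 df), two-sided 0.05, 1,000,000 simulated trials per setting. The difference d = 0.53 is simply what 56 per arm detects with about 80% power: noncentrality = n × d² / 2 = 56 × 0.53² / 2 = 7.87, which on 1 and 165 df gives 79.6%. *Pattern* means that Buzzy is significantly better than sham and vapocoolant is not. *Direct* means Buzzy significantly better than vapocoolant, tested after a significant 2-df arm test.

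Buzzy truly equal to vapocoolant:

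| Sham worse by (SD) | Overall test significant | Pattern | Direct |
|---|---|---|---|
| 0.3 | 35.0% | 15.3% | 2.1% |
| 0.4 | 57.4% | 16.3% | 2.3% |
| 0.53 | 82.7% | 11.4% | 2.5% |
| 0.6 | 91.2% | 7.6% | 2.5% |
| 0.8 | 99.4% | 1.1% | 2.5% |

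Buzzy truly 0.53 SD better than vapocoolant:

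| Sham worse than vapocoolant by (SD) | Both beat sham | Pattern | Direct |
|---|---|---|---|
| 0 | 2.5% | 77.1% | 75.2% |
| 0.27 | 29.4% | 69.4% | 79.4% |
| 0.53 | 79.6% | 20.4% | 79.6% |

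In the last row the pattern misses the advantage in 100 − 20.4 = 79.6% of trials, and the direct contrast in 100 − 79.6 = 20.4%.

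**5. Error control across three contrasts.** With all arms equal, testing all three pairs at 0.05 with no control gives at least one rejection in 12.15% of trials. Requiring a significant 2-df arm test first gives 5.02%. With two arms equal and the third 0.3 to 1.0 SD away, the false rejection rate under that rule is 4.1 to 5.0%. Power for Buzzy vs vapocoolant at d = 0.53 is 79.6% without the gate. With it, power is 69.0% (sham midway between the two), 75.1% (sham equal to vapocoolant) or 79.4% (sham 0.27 SD worse). The cost is therefore 79.6 − 79.4 = 0.2 to 79.6 − 69.0 = 10.6 points.

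**The case against.** The count is plainly a wording slip. Every design section and the power paragraph give three groups, so a reader who infers that the number of arms is in doubt, or that a six-group trial was intended, goes beyond the documents. On its own, the slip is a small correction in two places. That stands.

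An ANOVA fitted to three arms also supplies the estimate and standard error for Buzzy vs vapocoolant, and a statistician may well run that contrast. So the defect is an unnamed contrast, not the adoption of an invalid test. A reader might take the 11% and 80% figures as error rates of this trial. They are not: they measure an inference that no section states, under effects and sham positions that the documents do not give. At 0.8 SD the misleading pattern almost vanishes, and when sham equals vapocoolant the pattern does slightly better than the gated direct test (77% vs 75%).

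The chi-square test on no or mild pain, the only kind of test that section 17.2 powers, would include vapocoolant. But an overall chi-square does not isolate Buzzy vs vapocoolant either, and this correction leaves that test as it is.

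The word *or* in sections 1.2 and 2.1 could be read as letting a win over placebo alone suffice. Vapocoolant is still a named comparator there, and section 3.1 presents the comparison of the methods as the reason for the study.

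**Conclusion.** The point holds on the text alone. The ANOVA sentence, in both places, describes a number of interventions that the trial does not have, and with the number corrected the plan still names no test of Buzzy against vapocoolant, one of the two comparisons in its hypothesis and stated primary outcome. This must be corrected before the data are analysed.

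The consequence cannot be quantified from the documents, which give no SD, target difference or expected sham response for pain scores. The simulations show only that comparisons with sham can be a poor substitute for the direct contrast: at worst here, about 80% of real 0.53 SD advantages missed against about 20%; at best, no material difference.

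The choice of primary pain score, the role of the other raters (section 1.2 joins child, parent and observer) and the Kruskal-Wallis wording are separate matters. This point does not claim that any of them is an error.

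**What to change.** In section 17.1 and in the closing Data Management and Analysis text, replace the ANOVA sentence with:

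*Pain scores will be compared among the three randomised arms (Buzzy, vapocoolant, sham) by ANOVA, with prespecified contrasts Buzzy vs vapocoolant and Buzzy vs sham, and also vapocoolant vs sham.*

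Add a line stating how error is controlled across the contrasts; the choice is the sponsor's. Testing each contrast at two-sided 0.05 only after a significant 2-df arm test is one option. For three groups it holds the error rate at 0.05, at a cost of about 0 to 11 points of Buzzy-vs-vapocoolant power under the assumptions above. Keeping vapocoolant vs sham retains a comparison that the present sentence covers.

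The change needs no further patients, instruments or data: one sentence in two places and one line on error control.

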6.0 Inclusion and Exclusion Criteria

*6.1 Describe the criteria that define who will be **included** in your final study sample.*

NOTE: This may be done in bullet point fashion.

Response:

Inclusion criteria:

1. Male or female patients 6 to 18 years old

2. Need venipuncture procedure including IV's line placement and/or phlebotomy at the ED.

6.2 Describe the criteria that define who will be *excluded* from your final study sample.

NOTE: This may be done in bullet point fashion.

Response:

Exclusion criteria include:

1. Patients is sensitive to cold i.e. Raynaud's disease.
2. Sickle cell disease, diabetic
3. Critically ill patients
4. Mentally challenged patients
- 5.. GCS< 15
- 6.. Patient with altered sensation
- 7.. Patients needing more than one attempt for IV placement or phlebotomy

6.3 Indicate specifically whether you will include any of the following special populations in your study using the checkboxes below.

NOTE: Members of special populations may not be targeted for enrollment in your study unless you indicate this in your inclusion criteria.

Response:

- Adults unable to consent
- Individuals who are not yet adults (infants, children, teenagers)
- Pregnant women
- Prisoners

6.4 Indicate whether you will include non-English speaking individuals in your study. Provide justification if you will exclude non-English speaking individuals.

*In order to meet one of the primary ethical principles of equitable selection of subjects, non-English speaking individuals may **not** be routinely excluded from research as a matter of convenience.*

In cases where the research is of therapeutic intent or is designed to investigate areas that would necessarily require certain populations who may not speak English, the researcher is required to make efforts to recruit and include non-English speaking individuals. However, there are studies in which it would be reasonable to limit subjects to those who speak English. Some examples include pilot studies, small unfunded studies with validated instruments not available in other languages, studies with numerous questionnaires, and some non-therapeutic studies which offer no direct benefit.

Response:

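### Pain scores are compared by an ANOVA that names no covariate, although a before-procedure FPS-R is collected; prespecified ANCOVA would be at least as precise, provided the before-score precedes the intervention

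*Combined protocol and SAP*

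**What the plan says.** Section 10.1 plans paired pain ratings: "Before and after the venipuncture procedure, we will ask the legal guardian and subject to complete a Faces pain scale revised form". It does not place the before-rating relative to randomization or to application of the spray, device or sham.

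Section 17.1, repeated word for word in the Data Management and Analysis text at the end of the document, gives the whole plan for comparing pain scores between arms: "Comparisons of pain scores of the five intervention groups to placebo (sham device) will be analyzed via ANOVA". Neither place mentions a covariate, a regression model or a stratified analysis. Neither says whether a pain score here means the after-score or the before-to-after change. Section 2.1 words the primary outcome as a larger reduction in anxiety and pain, so a change score is a live reading.

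The population is mixed. Section 6.1 admits "Male or female patients 6 to 18 years old" who need "line placement and/or phlebotomy at the ED". Section 10.1 describes allocation from a statistician's table and mentions no stratification. Section 10.2 lists demographics, the reason for the venipuncture and the pain scores among the data to be collected. It names neither age nor procedure type.

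**The concern.** Children reach an emergency department with differing amounts of pain from whatever brought them in, and they range from early school age to 18. Variation of this kind that is left in the error term widens confidence intervals and lowers power. The trial already plans to measure part of it with the before-procedure FPS-R.

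The hypothesis in section 1.2 rests largely on child and parent report, so this comparison carries much of the efficacy claim. The unspecified outcome adds to the problem. If the analyst takes the reduction wording literally and analyses change scores, precision can be worse than if the before-score had never been collected.

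**Working it through.** **The plan's own figure.** Section 17.2 sizes the trial "based on a medium effect size of 0.3, alpha of 0.05, degree of freedom of 8, and 80% power". For a noncentral chi-square with 8 degrees of freedom, 80% power at 0.05 needs a noncentrality of 15.022. Then N = 15.022 / 0.3² = 166.9, so 167, or 168 in three equal arms, where power is 80.3%. The stated 168 reproduces. It is the size for a chi-square test, however, and says nothing about precision on the pain score.

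**Inputs for the pain-score comparison.**
- n = 56 per arm, from section 5.1: "We will enroll 168 patients in the study with 56 in each arm". All 56 are taken as analysed.
- Two-sided alpha of 0.05 for one contrast of Buzzy with a comparator. The 0.05 is from section 17.2; applying it to each contrast is an assumption.
- True difference d = 0.5 SD of the after-score. This is an assumption; the documents give no target difference and no SD.
- Before/after correlation r. The documents give none, so it is shown from 0.1 to 0.6.

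**Variance factors, relative to the after-score alone (factor 1).**
- ANCOVA on the before-score: 1 − r².
- Change score, with equal SDs before and after: 2(1 − r). This exceeds 1, and so is worse than ignoring the before-score, whenever r is below 0.5.
- The difference is 2(1 − r) − (1 − r²) = (1 − r)², which is never negative. If the before-score SD is k times the after-score SD, the change factor becomes 1 + k² − 2rk and the difference becomes (k − r)², also never negative. ANCOVA therefore never has the larger factor.

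**Power.** Noncentral t with noncentrality (d / √factor) × √(n/2), where √(56/2) = 5.292. Degrees of freedom are 110, or 109 with one covariate.
- After-score alone: 0.5 × 5.292 = 2.646, power 74.6%.
- Worked example at r = 0.3: ANCOVA 0.5/√0.91 × 5.292 = 2.774, power 78.5%; change score 0.5/√1.4 × 5.292 = 2.236, power 60.1%.

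| r | 1 − r² | ANCOVA power | Equivalent n per arm, 56/(1 − r²) | 2(1 − r) | Change-score power |
|---|---|---|---|---|---|
| 0.1 | 0.99 | 75.0% | 56.6 | 1.8 | 49.8% |
| 0.2 | 0.96 | 76.3% | 58.3 | 1.6 | 54.5% |
| 0.3 | 0.91 | 78.5% | 61.5 | 1.4 | 60.1% |
| 0.4 | 0.84 | 81.6% | 66.7 | 1.2 | 66.8% |
| 0.5 | 0.75 | 85.7% | 74.7 | 1.0 | 74.6% |
| 0.6 | 0.64 | 90.6% | 87.5 | 0.8 | 83.5% |

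**Sensitivity to d.** At 0.534 SD, where the after-score alone has 80% power, ANCOVA gives 81.6%, 83.6%, 89.9% and 93.8% at r = 0.2, 0.3, 0.5 and 0.6. The change score gives 60.1%, 65.8%, 80.0% and 87.9%. The pattern is the same.

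**The case against.** The strongest reply is that nothing here is an error. Under randomization, an ANOVA of the after-score is unbiased and keeps its type I error, and chance imbalance is already reflected in that error rate. This stands. A reader might infer that the planned comparison is invalid or biased; the documents do not support that.

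The gain may also be negligible. The before-score reflects presenting illness, or no pain at all, while the after-score reflects the needle, so a low r is plausible. At r = 0.2 the gain over the after-score alone is 76.3 − 74.6 = 1.7 points, worth 58.3 − 56 = 2.3 children per arm. This stands too, and it is why no single figure for lost power can be given.

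A reader might also infer that procedure type is recorded and then ignored. Section 10.2 does not list it, and the reason for a venipuncture is not the same as IV placement versus phlebotomy. The mention in section 6.1 is an eligibility term, and it allows a child to have both. The data form is not in the text, so the item may or may not be captured. Age is implied by demographics but not named.

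Nor does the plan say that the ANOVA is unadjusted; that is inferred from the absence of any covariate. On a change-score reading the before-score is used, only inefficiently.

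Finally, adjusting for a before-score is safe only if treatment cannot have affected it. The only definition of a pre-procedure period, given in section 17.1 for the PBCL, includes placement of the spray, device or sham. Section 3.1 cites the hypothesis that children feel the cold itself as painful. Adjusting for a score taken in that window could bias the comparison. This stands and shapes the fix.

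**Conclusion.** The point holds as one of efficiency and specification. The planned comparison is valid but avoidably imprecise, and its outcome is undefined. Whichever outcome was meant, ANCOVA on a before-score that precedes the intervention is at least as precise, apart from one degree of freedom.

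The size depends on an r that the documents do not give. With the assumed 0.5 SD difference, ANCOVA adds 0.4 points of power over the after-score alone at r = 0.1 (75.0 − 74.6) and 16.0 points at r = 0.6 (90.6 − 74.6). Against a change score the advantage is largest where r is low: 25.2 points at r = 0.1 (75.0 − 49.8), falling to 7.1 at r = 0.6 (90.6 − 83.5). These change-score figures assume equal SDs before and after. No gain has been quantified for age or procedure type. The change is worth making because it costs so little, not because a large loss has been shown.

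**What to change.** 1. In section 10.1, state that child and guardian complete the before FPS-R before randomization, and at the latest before any spray, device or sham is applied.

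2. In section 17.1 and in the repeated text at the end of the document, replace the ANOVA sentence with:

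> After-procedure FPS-R will be compared among the three arms by ANCOVA with the before-procedure FPS-R and age as covariates, reporting Buzzy minus vapocoolant and Buzzy minus placebo with 95% CIs.

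This also settles which pain score is analysed and removes the count of five intervention groups, which does not fit a three-arm trial.

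3. Use the same model for the guardian's FPS-R, with the guardian's own before-score.

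4. Add procedure type (IV placement, phlebotomy or both) as a covariate only if the data form records it.

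The cost is the revised analysis wording, one sentence on timing and one degree of freedom for each single-term covariate (two for a three-level procedure type). It needs no extra patients and no new instrument. If the before-score is at present taken after the intervention is applied, moving it is a small procedural change as well.
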